The dispensary will set aside a specific lot of each flower (to be smoked or vaporized) and edible form of the assigned strain, which will be packaged in childproof bottles and labeled as “Strain C”, “Strain D” or “Strain E”, such that participants and dispensary staff will be blind to the ratio assignment until the product is purchased (THC and CBD content will be printed on the label, as required by state law), and the research staff will remain blind to which strain was assigned until after data analysis. [name] (co-investigator) will maintain the blind during the study period. The instruction to purchase “C”, “D” or “E” will be randomized across participants such that equal numbers of male and female participants are included across the ratio conditions. The design involves the instruction that participants can use as little or as much of the marijuana as they wish over the course of the four weeks of the study, and are asked not to use any other strain during that time (but if so, to just report what was used). Therefore, a research assistant will give participants that are marijuana users, a card with directions to a local dispensary. The card will have instructions to purchase a particular strain of cannabis (e.g., “strain C”) but participants will choose the amount of cannabis that they expect to use during the study (i.e., we will not assign a specific amount for them to purchase or to use during the 4-week study period). While the potency may vary slightly by the strain assignment and the amount used may vary by each person, we expect approximately one gram of flower cannabis to cost \$12 and approximately 75mg of edible cannabis to cost \$15 (comparable across typical serving amount). However, this will depend in part on what cannabis type and how much cannabis each participant chooses to use. Study staff will not provide any directions regarding dosing and administration.

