Because the long-term goal of this work is to better understand the effect of different levels of cannabinoids in anxiety patients, as they are used real world, we decided that it was critically important to emphasize external validity in both the flower and edible forms of cannabis use. The disadvantage of our design is that we have little control over how the participants use the marijuana or how much they use. To address this limitation, both in our pilot study and in this application, we rely on blood quantitation of cannabinoids (from both flower and edible users) to determine the level of THC and CBD in each subject. Thus, regardless of how the participant uses the marijuana, we have an objective measure of the dose received for both THC and CBD for each subject, which is the sine qua non of pharmacological research. This aspect is also critical for our analytic approach, which allows for the analysis of THC and CBD blood levels as continuous measures. In this way, we also capitalize on the greater variability in blood levels expected in the design by analyzing overall levels of CBD and THC as well as by strain, which by design (in flower and edible forms) will have different THC/CBD ratios. This further allows for a direct test of whether any differences in outcomes for participants randomly assigned to the -THC/+CBD strain are due to an increase in CBD or a decrease in THC as compared to their Baseline. This strain is a critical comparison as there are data to suggest that the effects of THC differ when CBD is also in the blood.

**Power Analysis and Sample Size Requirements.** Sample size was selected to permit analysis of the primary research questions at two-tailed alpha of .05 and power level of .80. Estimates of effect size follow Cohen and were conducted in G\*Power 3. The primary analyses in **Aims 1-3** broadly is the test of the group X time interaction effects across repeated assessments of THC/CBD and anxiety, inflammatory markers, and stress reactivity. For the current data analysis plan, we will only focus on the ratios and time points that we currently have supporting preliminary data for and hypothesize to have the greatest impact on anxiety. Hence, in this data analysis plan we will focus on the 3 main time points (out of 4) for a chronic use endpoint [Baseline, 2 Week, and 4-Week Pre-administration (Sessions 1-3)] and the 3 main cannabis product so that there will be

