an all THC, all CBD, and a combination of THC to CBD group [(+THC/-CBD, +THC/+CBD, and -THC/+CBD, ratios: 1:0, 1:1, and 0:1)].

[figure not shown]
[figure not shown]
To be conservative, we thus estimated an ICC of .50. Using a mixed model ANOVA design, with four groups, three assessment points, and an average ICC = .5 between assessment points, a total  $n=450$  (75 per flower group and the control, and 50 per edible group) will allow us to detect a groupXtime interaction effect as small as  $f=.09$ . In **Aim 2B**, the test of the effects of group on stress-reactivity will again involve four groups ( 3 cannabis and 1 control) but only one assessment point.. Note that our power analysis is conservative, as our actual analysis will involve more powerful tests (e.g., focused interaction contrasts as opposed to overall  $F$  tests). For **Aim 3**, the estimation of the mediational model via path analysis (Hypothesis 3; see Figures 3a and 3b below), Monte Carlo simulation strategies formed the basis of our power analysis. Given that the model in Figure 3b is the more complex of the two, we utilized the model structure with the three planned contrasts as exogenous variables in our simulations. The key test of Hypothesis 3 will involve the use of structural equation modeling techniques. Because we have almost no empirical data on which to base estimates of effect size, we conservatively utilized small to moderate effect sizes depending upon hypothesized relationships. For example, we expect small coefficients (.20) from each contrast to stress reactivity, whereas we expect a slightly larger path (.40) between the contrast comparing the -THC/+CBD strain to control and inflammation. Power analyses were conducted in Mplus and then in SAS following procedures for estimating the power of the likelihood ratio test of the significance of parameters in structural equation models. We utilized Monte Carlo simulation to generate a population covariance matrix based on the hypothesized parameters in the model. For the smallest path in the model (which requires the most power to test), assuming two-tailed alpha of .05, our estimates of power at various sample sizes appear in Table 3. To assure .80 power or better to detect small associations between all groups, we thus require data from 450 participants (75 in the control and each flower group as well as 50 in each edible group) for our mediational analyses.

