**Specific Aim 1** – To compare changes in anxiety in mild to moderately anxious marijuana users exposed to 4 weeks of use of one of three different marijuana strains (+THC/-CBD vs. +THC/+CBD vs. -THC/+CBD) to a group of non-using controls matched on anxiety. *Hypothesis 1* predicts a main effect of strain such that -THC/+CBD marijuana users will have lower levels of anxiety (BAI) compared to other marijuana groups and to non-using controls. To examine the main effects of group on these outcomes, we will estimate a random coefficient regression (RCR) models in SAS Proc Mixed wherein the change in BAI scores will be regressed on marijuana user group, time, and the groupXtime interaction. *Hypothesis 1* also predicts that higher CBD levels in blood among marijuana users will be associated with lower BAI. The analysis for this hypothesis will again be a RCR model, but instead of group membership, the independent variables in these models will be level of CBD in blood, time, and the CBDxtime interaction. We will conduct additional models to explore whether there may also be main effects of THC in blood or a THCXCBD interaction effect on BAI. Secondary models will test the effects of strain and /or cannabinoid blood levels on the daily and monthly assessments of anxiety using a multi-level modeling approach. These additional analyses will appropriately control for Type I error, depending upon the number of tests run. Co-I [name] has used such models extensively in prior work.

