### **Criteria for inclusion in the study are:**

1. Must be between the ages of 21 and 70 and provide informed consent;
2. Must report at least moderate anxiety ( $\geq 5$  on GAD-7);
3. Users (cannabis group) must have used marijuana at least once;
4. Users (cannabis group) must have a desire to use marijuana to cope with anxiety;
5. Non-users (non-cannabis, control group) must not have used marijuana for prior 6 months;
6. Non-users (non-cannabis, control group) must not have a desire to use marijuana to cope with anxiety;
7. Must report not using other drugs (cocaine, methamphetamine) in the past 72 hours and must not test positive on a urine toxicology test for drugs of abuse at the Baseline Appointment;
8. Must not be using psychotropic, steroid-based medications, or maximal doses of non-steroidal anti-inflammatories (NSAIDs), however anti-depressants and ADHD medications are ok;
9. Must not have immune-relevant disease (e.g. HIV) or be using anti-viral medications;
10. Must not be a regular tobacco user ( $\leq 4$  days per week; cigarette, E-cigs, or smokeless);
11. Must have a breath alcohol level of 0 at screening (to sign consent form);
12. Must not be actively seeking or in treatment for any substance use disorder (drug use levels will be carefully monitored via Timeline Follow Back (TLFB) throughout the study to assess any confounding influences of drug or alcohol use);
13. Female subjects must not be or trying to become pregnant (as indicated by a Pregnancy test & Screening form administered at Baseline)
14. Must not be in treatment for psychotic disorder, bipolar disorder, or major depression disorder with suicidal ideation; or a history with these disorders.

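### The blood-CBD models rest on a partly self-chosen dose, without the randomised arm or a named baseline term, so they cannot give the causal test claimed for them; the bias can go either way

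*Combined protocol and SAP*

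**What the plan says.** **What is randomised.** Section XII (Baseline Appointment) randomises users to one of three THC:CBD ratios. Amount and timing are left to the participant: under Marijuana Administration at Home (Section IV), "participants can use as little or as much of the marijuana as they wish".

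**The models.** Specific Aim 1 of the Statistical Analysis Plan first regresses change in BAI on group, time and their interaction. For the blood-level half of Hypothesis 1 the group term is replaced: "the independent variables in these models will be level of CBD in blood, time, and the CBDxtime interaction". Hypothesis 2A repeats this, and Hypothesis 2B uses blood CBD as the predictor. Further models may add THC and a THC-by-CBD interaction. The outcome of the Aim 1 CBD model (level or change) is not restated. Baseline adjustment is mentioned only conditionally, in the BAI entry of Table 2.

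**The claim.** The Rationale for Marijuana Administration Procedure concedes limited control over use and offers blood quantitation as the remedy. It continues: "This further allows for a direct test of whether any differences in outcomes for participants randomly assigned to the -THC/+CBD strain are due to" more CBD or less THC relative to baseline.

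**Who is enrolled.** Section VI, item 4: "Users (cannabis group) must have a desire to use marijuana to cope with anxiety". Item 3 requires only that users have used it at least once.

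**The concern.** Measuring a dose objectively does not make it independent of the participant's state. Blood CBD has a randomised part (the ratio) and a self-selected part (how much was used). In a cohort that wants cannabis for anxiety, a link between anxiety and amount used is plausible, and the CBD models contain nothing that separates the two parts. The slope can then reflect why people used more or less, not what CBD did.

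The blood-level prediction is written into Hypotheses 1, 2A and 2B, and Aim 3 allows blood levels as exogenous predictors in the mediation model. A confounded slope could hide a real effect or produce a false one, including one that favours the hypothesis.

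**Working it through.** **1. The plan's own figure.** No power figure is given for the CBD slope. The nearest is for the group comparison: "two-tailed alpha of .05 and power level of .80"; "75 per flower group and the control, and 50 per edible group"; "average ICC = .5 between assessment points"; and the design "will allow us to detect a groupXtime interaction effect as small as" f = .09. With λ = f²·N·m/(1 − ICC) = .0081 × 450 × 3/.5 = 21.87 and df 6 and 892, power is .958; the detectable f at power .80 is .071. The stated .09 fits N = 300 (4 × 75): λ = 14.58, power .826. So the figure is not reproduced at 450, but it errs on the safe side and has no bearing here.

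**2. Inputs to the illustration.**
- From the documents: 75 + 50 = 125 users per ratio, so n = 375; flower CBD contents 0, 12 and 18%, that is 0, 2/3 and 1 in relative terms; correlation .5 between assessments.
- Assumed: blood CBD = content × use; use lognormal with log-SD 0.8; correlation ρ of log-use with anxiety from .1 to .3; anxiety SD 1; no true CBD effect.

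**3. Size of the bias, cross-sectional.**
- E(use) = exp(.32) = 1.377; Var(use) = exp(.64) × (exp(.64) − 1) = 1.700.
- Mean content .5556; mean squared content .4815.
- Var(CBD) = .4815 × (1.700 + 1.377²) − (.5556 × 1.377)² = 1.146; SD 1.071.
- Cov(anxiety, CBD) = .5556 × ρ × .8 × 1.377 = .612ρ.
- Spurious slope per SD of CBD = .612ρ/1.071 = .57ρ; SE ≈ 1/√375 = .0516.

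| ρ | slope | slope/SE | significant, normal approximation | significant, simulated |
|---|---|---|---|---|
| .1 | +.057 | 1.11 | 20% | 22% |
| .2 | +.114 | 2.21 | 60% | 60% |
| .3 | +.171 | 3.32 | 91% | 91% |

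If the true slope were −0.30, the expected estimate is −.30 + .57ρ = −0.24, −0.19 and −0.13. Adding THC to the model does not help (simulated −0.24, −0.18, −0.12), because THC intake is self-chosen in the same way.

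**4. Direction.** Let ρ₀ and ρ₄ be the correlations of log-use with baseline and week-4 anxiety. The bias is about .57ρ₄ on level, .57(ρ₄ − ρ₀) on change, and .57(ρ₄ − .5ρ₀) after adjustment for baseline. At a correlation of .2:

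| What drives use | ρ₀, ρ₄ | level | change | baseline-adjusted |
|---|---|---|---|---|
| Current anxiety | 0, .2 | +.11 | +.11 | +.11 |
| Stable trait anxiety | .2, .2 | +.11 | 0 | +.06 |
| Baseline anxiety | .2, .1 | +.06 | −.06 | 0 |
| Less anxious now use more | 0, −.2 | −.11 | −.11 | −.11 |

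A separate simulation (slope per SD of log CBD, log-SD of use 0.7) shows the same pattern. At .2 with current anxiety driving use, the slope is +0.08 on level and on change, with 32–34% false positives. With trait anxiety it is +0.08 on level (35%) and 0.00 on change (6%). Use driven by baseline anxiety again reverses the sign between level and change. A repeated-measures CBD-by-time model gave +0.09 and 65% false positives in the current-anxiety case, from only 40 replicates.

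Adding arm to the blood-level model raises the current-anxiety bias to +0.17 to +0.18, because it removes the randomised share of the CBD variation. Comparing randomised arms with baseline adjustment stays at about 0.00, with 4–8% false positives.

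**5. Assigned ratio as an instrument.**
- CBD only: the between-arm share of CBD variance is .1728 × 1.377²/1.146 = .286, so the SE grows by 1/√.286 = 1.9 (simulated .094 against .051, about 1.8).
- CBD and THC together: contents (0, 2/3, 1) and (1, 2/3, 0) correlate −.93 across arms, leaving 1 − .929² = .138. The SE grows by 1/√(.286 × .138) = 5.0 (simulated about 5, with power .13–.17 at a true slope of −0.30).

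**The case against.** The plan has a fair defence. The hypotheses are worded as associations, and Section I places them alongside strain assignment, not in its stead. Group models are planned separately for Aims 1, 2A and 2B. The lack of control over use is stated openly. Part of the blood-CBD variation is randomised, which dilutes the bias when arms are pooled. The causal over-reading sits largely in one sentence of the rationale. All of this stands, and it limits the seriousness. It does not supply the missing covariates or make that sentence true.

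A reader might infer more than the documents support:
- That the slope is biased towards CBD raising anxiety. That needs current anxiety to drive use, or BAI level to be the outcome. The Aim 1 group model uses change in BAI, for which trait-driven use gives about no bias and baseline-driven use gives the opposite sign. Stopping because of anxious reactions would also push the other way.
- That users were enrolled as established coping users. Entry requires a desire and at least one past use. A criterion shared by all users does not by itself create a gradient of dose with anxiety among them.
- That the sign carries over to inflammation and stress reactivity. That needs further assumptions, and neither was simulated.

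**Conclusion.** The point holds as a problem of confounding with uncertain direction. As written, the blood-CBD models cannot tell whether arm differences are due to more CBD or less THC, and their false-positive rate can be far above 5% (about 22–91% for assumed correlations of .1 to .3). These sizes rest on an assumed spread of use and an assumed link between anxiety and amount used; the documents give neither, and with no such link this bias disappears. The comparison of randomised ratios is unaffected by choice of dose. This should be corrected before analysis, but it does not undermine the trial's main comparison.

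**What to change.** 1. Name the comparison of randomised ratios, adjusted for the baseline outcome, as the causal test in Aims 1, 2A and 2B. Reword the sentence in the Rationale for Marijuana Administration Procedure so that blood levels are described as supporting evidence on mechanism.
2. Keep the blood-level models and label them associational. State whether the outcome is level or change; prespecify baseline outcome, prior use and product type (flower or edible) as covariates; and split CBD into person-mean and within-person deviation. Baseline adjustment removes the bias from baseline-driven use, but only half of it for trait-driven use and none for current-anxiety-driven use, so the associational label is still needed.
3. Optionally, report two-stage least squares with assigned ratio as instrument, as a sensitivity analysis only. The CBD-only version costs an SE about 1.8 times larger and credits the whole ratio effect to CBD. The two-exposure version costs about 5 times and has little power. Both assume that ratio acts only through the modelled blood levels. That is doubtful here, because the THC and CBD content is printed on the label (Marijuana Administration at Home), so expectation could affect self-reported anxiety.

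The cost is a little more analysis on data already collected, and a weaker claim about mechanism.
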